3. OBJECTIVES AND ENDPOINTS

Objectives	Endpoints
Primary	
Pharmacokinetics Part A: 
To estimate the relative bioavailability of 100 mg/mL IM sotrovimab at the dorsogluteal injection site relative to the 62.5 mg/mL formulation administered dorsogluteally through Day 29
	Sotrovimab PK parameters: AUCD1-29 and Cmax
Safety Part A: 
To evaluate the safety and tolerability profile of 100 mg/mL IM sotrovimab and the 62.5 mg/mL formulation at the dorsogluteal injection site through Day 29
 Part C: 
 • To evaluate the safety and tolerability profile of IV sotrovimab in Cohort 1 and/or Cohort 2 through Day 29 	Incidence of all AEs, SAEs, and AESI through Day 29
Secondary	
Pharmacokinetics Part A: 
 • To estimate the relative bioavailability of 100 mg/mL IM sotrovimab at 2 alternative injection sites (anterolateral thigh and deltoid) relative to the 62.5 mg/mL formulation administered dorsogluteally through Day 29 Part B: 
 • To estimate the relative bioavailability of 100 mg/mL and/or 62.5 mg/mL IM sotrovimab at up to 2 injection sites 	Sotrovimab PK parameters: AUCD1-29 and Cmax

Objectives	Endpoints

relative to the 62.5 mg/mL formulation administered dorsogluteally through Day 29
 
Part C:
 
 • To characterize the PK of IV sotrovimab in Cohort 1 and/or Cohort 2 through Day 29 	

Pharmacokinetics
 
Part A:
 
 • To estimate the relative bioavailability of 100 mg/mL IM sotrovimab at 3 injection sites (dorsogluteal, anterolateral thigh, and deltoid) relative to the 62.5 mg/mL formulation administered dorsogluteally through Week 24 
Part B:
 
 • To estimate the relative bioavailability of 100 mg/mL and/or 62.5 mg/mL IM sotrovimab at up to 2 injection sites relative to the 62.5 mg/mL formulation administered dorsogluteally through Week 24 	Sotrovimab PK parameter: AUC _{inf}

Pharmacokinetics
 
Part A and Part B:
 
 • To characterize the PK of 100 mg/mL and 62.5 mg/mL IM sotrovimab through Day 29 and Week 24 
Part C:
 
 • To characterize the PK of IV sotrovimab in Cohort 1 and/or Cohort 2 through Day 29 and Week 24 	
 • Serum PK of sotrovimab

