8.4.1. Time Period and Frequency for Collecting AE and SAE Information

- All AEs and SAEs will be collected from dose administration until Week 35 at the timepoints specified in the SoA (Section 1.3). However, any SAEs assessed as related to study participation (e.g., study intervention, protocol-mandated procedures, invasive tests, or change in existing therapy) or related to a GSK product will be recorded from the time a participant consents to participate in the study.
- Medical occurrences that begin before the start of study intervention but after obtaining informed consent will be recorded as medical history/current medical conditions not as AEs.
- All SAEs will be recorded and reported to GSK immediately and under no circumstance should this exceed 24 hours, as indicated in Section 10.3. The investigator will submit any updated SAE data to GSK within 24 hours of it being available.
- Investigators are not obligated to actively seek information on AEs or SAEs after conclusion of the study participation. However, if the investigator learns of any SAE, including a death, at any time after a participant has been discharged from the study, and he/she considers the event to be reasonably related to the study intervention or study participation, the investigator must promptly notify GSK.

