9.3.2.2. Safety**Table 8 Primary Estimand of the Primary Safety Endpoint****Part A:**

Primary Estimand	
Population	Male or female healthy participants aged 18 to 65 years
Variable/Endpoints	Incidence of all AEs, SAEs, and AESI through Day 29 (i.e., all events on the database at the time of DCO)
Treatment	100 mg/mL IM sotrovimab and 62.5 mg/mL IM sotrovimab (dorsogluteal injections)
Strategy for Intercurrent Events or Events Leading to Missing Data	The intercurrent event of interest is participants receiving incomplete IM dose. The strategy for handling this intercurrent event will be a Treatment Policy Strategy, where all safety data after the intercurrent event will be included. Missing data will not be imputed.
Population-Level Summary	Frequency and percentages of participants

Part C Cohort 1:

Primary Estimand	
Population	Male or female healthy participants aged 18 to 65 years
Variable/Endpoints	Incidence of all AEs, SAEs, and AESI through Day 29 (i.e., all events on the database at the time of DCO)
Treatment	Single IV infusion of sotrovimab at 3000 mg dose
Strategy for Intercurrent Events or Events Leading to Missing Data	The intercurrent event of interest is participants receiving incomplete IV dose. The strategy for handling this intercurrent event will be a Treatment Policy Strategy, where all safety data after the intercurrent event will be included. Missing data will not be imputed.
Population-Level Summary	Frequency and percentages of participants

For Part C optional Cohort 2, similar Estimand strategy will be followed for treatment:
Single IV infusion of sotrovimab at up to 3000 mg dose.

Occurrence of AEs, SAEs, and AESIs will be displayed in the form of summaries and listings using the Safety population. Further details will be provided in the SAP.

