1.1. Objectives, Estimands and Endpoints

Objectives	Endpoints
Primary	
Pharmacokinetics Part A: To estimate the relative bioavailability of 100 mg/mL IM sotrovimab at the dorsogluteal injection site relative to the 62.5 mg/mL formulation administered dorsogluteally through Day 29	Sotrovimab pharmacokinetics (PK) parameters: AUC_{D1-29} and C_{max}
Safety Part A: To evaluate the safety and tolerability profile of 100 mg/mL IM sotrovimab and	Incidence of all adverse events (AEs), serious adverse events (SAEs), and adverse events of special interest (AESI) through Day 29

Objectives	Endpoints

the 62.5 mg/mL formulation at the dorsogluteal injection site through Day 29
 
Part C:
 
To evaluate the safety and tolerability profile of IV sotrovimab in Cohort 1 through Day 29
	
Secondary	

Pharmacokinetics
 
Part A:
 
To estimate the relative bioavailability of 100 mg/mL IM sotrovimab at 2 alternative injection sites (anterolateral thigh, and deltoid) relative to the 62.5 mg/mL formulation administered dorsogluteally through Day 29
 
Part C:
 
To characterize the PK of IV sotrovimab in Cohort 1 through Day 29
	Sotrovimab PK parameters: AUC_{D1-29} and C_{max}

Pharmacokinetics
 
Part A:
 
To estimate the relative bioavailability of 100 mg/mL IM sotrovimab at 3 injection sites (dorsogluteal, anterolateral thigh, and deltoid) relative to the 62.5 mg/mL formulation administered dorsogluteally through Week 24
	Sotrovimab PK parameter: AUC_{inf}

Pharmacokinetics
 
Part A:
 
To characterize the PK of 100 mg/mL and 62.5 mg/mL IM sotrovimab through Day 29 and Week 24
	Serum PK of sotrovimab

Objectives	Endpoints

Part C:
 
To characterize the PK of IV sotrovimab in Cohort 1 through Day 29 and Week 24
	

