- Population: Male or female healthy participants aged 18 to 65 years who would be able to complete the IM dose.
- Endpoints: Sotrovimab serum PK parameters: AUC_{D1-29} and C_{max} .
- Treatments: 100 mg/mL IM sotrovimab vs 62.5 mg/mL IM sotrovimab (dorsogluteal injections).
- Strategy for intercurrent event: The intercurrent event of interest is participants receiving an incomplete IM dose. The strategy for handling this intercurrent event will be a Principal Stratum Strategy, where we are only interested in the strata of participants who would be able to receive a complete IM dose. Exclusion of participants who did not receive a complete IM dose will not introduce bias as the reasons for dose interruption are not related to their PK.
- Population-level summary: The point estimate for the ratio of the geometric means of 100 mg/mL treatment group compared to the 62.5 mg/mL treatment group and the related 90% confidence interval (CI) will be calculated.

The Safety primary estimand is described by the following attributes:

- Population: Male or female healthy participants aged 18 to 65 years.
- Endpoints: Incidence of all AEs, SAEs, and AESI through Day 29 (i.e., all events on the database at the time of data cut-off [DCO]).
- Treatments: 100 mg/mL IM sotrovimab and 62.5 mg/mL IM sotrovimab (dorsogluteal injections).
- Strategy for intercurrent event: The intercurrent event of interest is participants receiving an incomplete IM dose. The strategy for handling this intercurrent event will be a Treatment Policy Strategy, where all safety data after the intercurrent event will be included.
- Population-level summary: Frequency and percentage of participants.

Primary Estimand (Part C)

The primary clinical question of interest is: what is the safety and tolerability of IV infusion of sotrovimab at 3000 mg dose in Cohort 1?

The Safety primary estimand is described by the following attributes:

- Population: Male or female healthy participants aged 18 to 65 years.
- Endpoints: Incidence of all AEs, SAEs, and AESI through Day 29 (i.e., all events on the database at the time of DCO).

[figure not shown]
- Treatments: Single IV infusion of sotrovimab at 3000 mg dose in Cohort 1.
- Strategy for intercurrent event: The intercurrent event of interest is participants receiving an incomplete IV dose. The strategy for handling this intercurrent event will be a Treatment Policy Strategy, where all safety data after the intercurrent event will be included.

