4.2.2.2. Definition of Endpoint(s)

The primary safety endpoints for the primary safety objectives (Part A: safety and tolerability of 100 mg/mL and 62.5 mg/mL IM sotrovimab at the dorsogluteal injection sites; Part C: safety and tolerability of IV sotrovimab) are:

- Incidence of AEs through Day 29
- Incidence of SAEs through Day 29
- Incidence of AESIs through Day 29

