4.2.2.3. Main Analytical Approach

The analyses described in the following sections, will be performed using the Safety analysis set in all study parts, as defined in Section 3. Unless otherwise specified, available data will be analyzed as collected regardless of intercurrent events that may occur (treatment policy). Missing data will not be imputed.

Incidence of AEs, SAEs, and AESIs through Day 29 will be displayed in the form of summaries and listings, where appropriate. Further details are provided below.

Adverse Events

Adverse events will be coded using Medical Dictionary for Regulatory Activities (MedDRA) central coding dictionary. Adverse events analyses including the analysis of AEs, SAEs and other significant AEs will be based on GSK Core Data Standards.

Adverse event displays to be generated include: overview of AEs, all AEs, all SAEs, AEs leading to permanent discontinuation of study treatment or permanent withdrawal from study, common ($\geq 5\%$) AEs, common ($\geq 5\%$) Non-Serious AEs, common ($\geq 5\%$) SAEs, Drug-related AEs, Serious Drug-related AEs, Non-Serious Drug-related AEs, and Adverse events leading to withdrawal. For Part C, common ($\geq 1\%$) AEs, common ($\geq 1\%$) Non-Serious AEs, common ($\geq 1\%$) SAEs may be additionally reported. The number and percentages of participants with the event will be summarized by System Order Class (SOC) and Preferred Term (PT), unless otherwise specified in the [OPS](#). Adverse Events including fatal SAEs and AEs leading to withdrawal will also be listed as specified in the [OPS](#).

A drug-related AE is defined as an AE for which the investigator classifies the relationship to study intervention as “Yes”. A worst-case scenario approach will be taken to handle missing relatedness data, i.e. the summary table will include events with the relationship to study intervention as ‘Yes’ or missing.

Adverse Events of Special Interest

Adverse events of special interest will be monitored by GSK at Day 29 and either during or at the end of the study (through Week 35). These will be updated during the course of the study based on accumulating safety data.

Adverse event of special interest includes:

- Hypersensitivity reactions occurring any time post dose

- Infusion-related reactions within 24 hours post dose (Part C)
- Injection site reactions (Part A)
- Immunogenicity
- AEs potentially related to antibody-dependent enhancement of disease

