4.3.2.3. Main Analytical Approach

The analyses will be performed using the Safety analysis set in all study parts, as defined in Section 3. Unless otherwise specified, available data will be analyzed as collected regardless of intercurrent events that may occur (treatment policy). Missing data will not be imputed.

Adverse Events, Serious Adverse Events and Adverse Events of Special Interests

Occurrence of AEs, SAEs, and AESIs through Week 35 will be displayed in the form of summaries and listings, where appropriate.

Unless otherwise specified, the secondary safety endpoints will be analyzed as described in Section 4.2.2.2 for the primary safety endpoints.

Vital Signs

Vital sign data include temperature, pulse rate (PR), oxygen saturation (SpO₂), respiratory rate, and blood pressure.

Summary statistics for all results and changes from baseline will be provided in a table by visit for each test. For each test, worst case for each participant will also be summarized by visit. In addition, number of participants with increase in maximum grade from baseline will be summarized by visit for each parameter in a table. A shift table will also be generated to present the shift in post-baseline maximum grade from baseline by visit and overall worst-case post-baseline.

All vital sign data, as well as participants with abnormalities of potential clinical importance and grade will be provided in listings.

Clinical Laboratory Data

Clinical laboratory tests to be performed are listed in Appendix 3. For laboratory tests including hematology, coagulation, clinical chemistry and urinalysis, baseline, post-baseline and change from baseline results will be summarized by treatment arms.

Based upon laboratory normal ranges, the laboratory test results will be categorized according to the normal range provided by local lab as: “low” (below the lower limit), “normal” (within the normal range) and “high” (above the upper limit). The shift on worst-case post-baseline categories of laboratory result from baseline for each parameter will be summarized by visit in a table.

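### The primary safety estimand equates the Day 29 window with everything on the database at data cut-off, which is a different and longer window for most participants

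*Protocol*

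**What the plan says.** The estimand text carries the data cut-off (DCO) clause in both documents and for both study parts. Protocol Table 8 (Section 9.3.2.2), for Part A and for Part C Cohort 1, gives the variable as "Incidence of all AEs, SAEs, and AESI through Day 29 (i.e., all events on the database at the time of DCO"). The Protocol Section 3 estimand bullets and SAP Table 2 repeat it, and the SAP 1.1 bullets read "through Day 29 (i.e., all events on the database at the time of data cut-off [DCO"]).

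Elsewhere the same endpoint has no such clause:

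- Protocol Section 3, objectives table: "Incidence of all AEs, SAEs, and AESI through Day 29".
- SAP 1.1, objectives table: "Incidence of all adverse events (AEs), serious adverse events (SAEs), and adverse events of special interest (AESI) through Day 29".
- SAP 4.2.2.2, where the endpoint is formally defined: "Incidence of AEs through Day 29", with matching lines for SAEs and AESIs.
- SAP 4.2.2.3, the analysis statement: "Incidence of AEs, SAEs, and AESIs through Day 29 will be displayed in the form of summaries and listings".

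On timing, Protocol 8.4.1 states "All AEs and SAEs will be collected from dose administration until Week 35". SAP 4.7 triggers the Day 29 readout once the last recruited participant of the part or cohort has completed Day 29. SAP 4.8 declares no departure from the protocol analyses.

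**The concern.** A primary estimand should have one time window, and this one has two. A programmer working from the estimand tables would count every event on the database at the cut. One working from SAP 4.2.2.2 would stop at Day 29. The resulting primary tables could differ.

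The literal version gives a crude percentage over unequal follow-up: longest for the first participants dosed and 29 days for the last. That matters most in Part C Cohort 1, where the absolute percentage with an AE, SAE or AESI is the primary result and there is no concurrent arm. The percentage would then depend partly on how quickly sites enrolled, and the Day 29 primary endpoint would take in events that belong to the Week 35 secondary endpoint.

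**Working it through.** **Step 1. Can the two definitions coincide?** Only if nobody has follow-up beyond Day 29 at the cut. Collection runs to Week 35 (Protocol 8.4.1) and the cut follows the last participant's Day 29 (SAP 4.7), so everyone dosed earlier has later follow-up. In Part C Cohort 1 the design forces a gap. Protocol 4.1 requires about 30 participants to complete at least Day 8, and the safety review to finish, before anyone else is dosed. Those 30 are therefore about 7 days or more ahead, at about Day 36 or later when the last participant reaches Day 29.

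**Step 2. Is the clause a window definition at all?** The same parenthetical follows the Part C Week 35 endpoint (Protocol Table 12, SAP Table 8). There it does little harm, because scheduled collection ends at Week 35. One clause cannot define both windows.

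**Step 3. The plan's own Part C figure.** With n = 200 and a true rate of 1.14% (Protocol 9.5), the chance of at least one event is 1 − (1 − 0.0114)^200 = 0.899, against the stated 90%. The six 95% intervals for n = 200 also reproduce. These depend only on n and the rate or count, so the wording does not affect them.

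**Step 4. Size from the design alone.** Taken from the documents: about 30 of 200 participants are at least about 7 days ahead. Assumed: a true Day 29 incidence of 20%, a constant hazard to Day 29, a later hazard equal to a fraction r of it, and no accrual spread other than the hold.

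- Daily hazard: h = −ln(1 − 0.20)/29 = 0.00769.
- Lead-in participants: 1 − exp(−h × (29 + 7r)). The other 170 stay at 0.20.
- r = 0: 20.0%, no change.
- r = 0.25: lead-in 0.2107; overall (30 × 0.2107 + 170 × 0.20)/200 = 0.2016, about 20.2%.
- r = 1: lead-in 0.2420; overall (30 × 0.2420 + 170 × 0.20)/200 = 0.2063, about 20.6%.

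This is a floor for each r. Review time and ordinary accrual spread both lengthen follow-up, and the documents give neither duration.

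**The case against.** The strongest reply is that the parenthetical only names the data snapshot: Day 29 events, as entered by the cut. The fixed window stands where the SAP formally defines and analyses the endpoint, and SAP 4.7 describes the analysis as a readout of Day 29 endpoints. Display details are deferred to the output specification, which may already filter by onset. No formal hypothesis rests on safety, events are listed, and a literal count adds events rather than hiding them.

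Much of this stands. The intent may well have been benign, and no wrong output has been shown. It does not rescue the wording, because the clause is introduced as an equivalence and sets no onset limit. Nor is the literal reading far-fetched: SAP 4.6 applies an all-available-data rule to the Part C interim analysis, while limiting PK data there to Day 29. No visible passage gives an onset cut for the Day 29 AE tables.

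Two stronger readings are tempting but unsupported.

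- A reader might infer a large inflation of the Part C rates. Under uniform accrual without the hold and an undiminished later hazard, an assumed 20% would become 28.6% with 30-day accrual and 35.9% with 60-day accrual. Those accrual lengths, the hazard and the 20% are all assumptions, and with no later hazard nothing changes.
- A reader might take SAP 4.3.2.3, which says "the secondary safety endpoints will be analyzed as described in Section 4.2.2.2 for the primary safety endpoints", as fixing a Day 29 cut for the thigh and deltoid arms. Its AE sentence covers Week 35 only. The Day 29 endpoint for those arms is defined in SAP 4.3.2.2.

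**Conclusion.** The inconsistency is real and should be fixed. The estimand wording is wrong as written, because for anyone dosed before the last participant the database at cut-off extends past Day 29. If followed literally, it makes the Part C Cohort 1 primary percentages depend on enrolment speed.

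The size cannot be determined from the documents. The lead-in hold supports a shift from an assumed 20% to about 20.2-20.6% at a later hazard of 25-100%, with an unknown addition from accrual.

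Not affected: infusion-related reactions, which are limited to 24 hours after dosing; the 90% detection figure; the confidence-interval tables; and, in expectation, the randomized Part A contrasts, since concurrent randomization balances the extra follow-up between arms. Part A absolute percentages could still move.

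**What to change.** In the Protocol Section 3 estimand bullets (Parts A and C), Protocol Table 8, the SAP 1.1 estimand bullets and SAP Table 2, replace the parenthetical with: *events with onset from the start of dosing through Day 29, as recorded on the database at DCO*. The lower bound is needed because Protocol 8.4.1 records related SAEs from consent. Then:

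- Apply the same onset cut to the thigh and deltoid Day 29 summaries defined in SAP 4.3.2.2.
- State whether the upper limit is calendar Day 29 or the participant's actual Day 29 visit, which has a window of ±2 days.
- Place partial onset dates by comparing the SAP 6.2.6 imputed start date with that calendar limit. Do not derive a study day from it, because SAP 6.2.6 rules that out.
- SAP 6.2.6 does not impute a completely missing onset date. Count such events as in-window unless other data exclude it, such as a full end date before dosing.
- Report later-onset events under the Week 35 endpoint. The Week 35 rows (Protocol Table 12, SAP Table 8) can stay.

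The cost is a few text edits in two documents and one onset-date filter in the Day 29 AE programs, if it is not already there. No new data are needed and the sample size does not change.

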9.3.3. Secondary Endpoint(s)

9.3.3.1. Pharmacokinetics

Table 9 Primary Estimand for Secondary Pharmacokinetics Endpoint (Part A)

Primary Estimand	
Population	Male or female healthy participants aged 18 to 65 years who would be able to complete the IM dose
Variable/Endpoints	
 • AUC_{D1-29} and C_{max} through Day 29 • AUC_{inf} through Week 24 • Serum PK of sotrovimab through Day 29 and Week 24
Treatment Conditions	
 • AUC_{D1-29} and C_{max} through Day 29: 100 mg/mL sotrovimab (anterolateral thigh, deltoid) vs 62.5 mg/mL sotrovimab (dorsogluteal) • AUC_{inf} through Week 24: 100 mg/mL IM sotrovimab at three injection sites (dorsogluteal, anterolateral thigh, and deltoid) compared to the 62.5 mg/mL formulation administered dorsogluteally • Serum PK of sotrovimab through Day 29 and Week 24: 100 mg/mL and 62.5 mg/mL IM sotrovimab
Strategy for Intercurrent Events or Events Leading to Missing Data	The intercurrent event of interest is participants receiving an incomplete IM dose. The strategy for handling this intercurrent event will be a Principal Stratum Strategy, where we are only interested in the strata of participants who would be able to receive a complete IM dose. Exclusion of participants who did not receive a complete IM dose will not introduce bias as the reasons for dose interruption are not related to their PK.
Population-Level Summary	
 • AUC_{D1-29} and C_{max} through Day 29: The point estimate for the ratio of the geometric mean of 100 mg/mL treatment group compared to the 62.5 mg/mL treatment group and the related 90% CI will be calculated • AUC_{inf} through Week 24: The point estimate for the ratio of treatment group geometric means and the related 90% CI will be calculated • Serum PK of sotrovimab through Day 29 and Week 24: geometric mean

The estimand strategy for secondary PK endpoints, including those for Part B, will be similar to the strategy described above; further details will be provided in the SAP.

Table 10 Primary Estimand for Secondary Pharmacokinetics Endpoint (Part C Cohort 1)

Primary Estimand	
Population	Male or female healthy participants aged 18 to 65 years who would be able to complete the IV dose
Variable/Endpoints	
 • AUC_{D1-29} and C_{max} through Day 29 • Serum PK of sotrovimab through Day 29 and Week 24
Treatment Conditions	
 • AUC_{D1-29} and C_{max} through Day 29: Single IV infusion of sotrovimab at 3000 mg dose • Serum PK of sotrovimab through Day 29 and Week 24: Single IV infusion of sotrovimab at 3000 mg dose
Strategy for Intercurrent Events or Events Leading to Missing Data	The intercurrent event of interest is participants receiving an incomplete IV dose. The strategy for handling this intercurrent event will be a Principal Stratum Strategy, where we are only interested in the strata of participants who would be able to receive a complete IV dose. Exclusion of participants who did not receive a complete IV dose will not introduce bias as the reasons for dose interruption are not related to their PK.
Population-Level Summary	
 • AUC_{D1-29} and C_{max} through Day 29: geometric mean • Serum PK of sotrovimab through Day 29 and Week 24: geometric mean

For Part C optional Cohort 2, similar Estimand strategy will be followed for treatment: Single IV infusion of sotrovimab at up to 3000 mg dose.

